10.2 Training of Staff

A formal meeting (Investigator’s meeting) will be conducted prior to site initiation. During this meeting, the Sponsor or its authorized representative will discuss the requirements of the clinical study protocol and related documents and will also provide training including a formal GCP training in the relevant systems and other study-specific procedures. The activities of the Investigator’s meeting will be described in the monitoring plan.

In addition to the Investigator meeting, the Investigator or designee will ensure that appropriate training relevant to the study is provided to all staff involved in the study, and

Confidentiality statement: Data and information contained in this document are considered to constitute trade secrets and confidential commercial information, and the legal protections provided to such trade secrets and confidential information are hereby claimed under the applicable provisions of applicable law. No part of this document may be publicly disclosed without the written consent of Philip Morris Products S.A.

that any new information relevant to the performance of this study is forwarded to the staff involved in a timely manner. The Investigator or designee will maintain a record of all individuals involved in the study.

10.3 Audits and Inspections

Good Clinical Practice regulations require that there are independent inspections of clinical program activities. Such inspections may be performed at any time before, during, and/or after the study.

Authorized representatives of the Sponsor, regulatory agencies, and/or an IEC may perform audits or inspections, including source data verification. The purpose of an audit or inspection is to systematically and independently examine all study-related activities and documents to determine whether these activities were conducted, and data were recorded, analyzed, and accurately reported according to the protocol, ICH/GCP guidelines, and any applicable regulatory requirements. The Investigator or designee will contact the Sponsor or the authorized representative immediately, if contacted by a regulatory agency about an inspection at their site.

The Investigator or designee and study staff are responsible for maintaining a comprehensive and accurate filing system of all study-related documentation that will be suitable for inspection at any time by the Sponsor, its authorized representative, and/or regulatory agencies. In signing this protocol, the Investigator or designee understands and agrees to provide access to the necessary documentation and files.

11 DATA MANAGEMENT ACTIVITIES

All Data Management Activities will be described in detail in the Data Management Plan (DMP) and documents specified therein.

11.1 Data Capture

11.1.1 Case Report Forms and Study Records

With the exception of the subject reported outcome data, all results from the clinical assessments will be recorded in the Source Documents by the Investigator or their authorized designee and then captured in the eCRFs at the study site. The subject questionnaires and the VAS will be entered by the subject directly in the ePRO device or a paper copy. Trained study personnel will be responsible for capturing the data from the observations, tests, and assessments specified in the protocol in the Source Documents and then transferring the data into the eCRF according to the eCRF Completion Guidelines.

The Investigator or designee has ultimate responsibility for the collection and reporting of all data related to the clinical study and ensuring that the data are accurate, authentic/original, legible, timely (contemporaneous), enduring, and available when required. The eCRF must be signed by the Investigator or designee to attest that the data contained in the eCRF are true and accurate. Any corrections made to Source Documents must be clearly recorded, without obscuring the original values and be accompanied by the date of change, reason for change, and identification of the person making the change. The eCRF for each subject will be checked against the Source Documents at the study site by the CRA. Instances of missing or unclear data will be discussed with the Investigator or designee for resolution. An eCRF will be generated for all subjects that sign the informed consent.

11.1.2 Protocol Deviations

All protocol deviations will be entered into the Clinical Trial Management System (CTMS) or other approved format.

Information from the Source Documents will represent the primary source of protocol deviations. Information following site monitoring and other manual reviews will be documented in the site visit reports, follow-up letters, audit documentation, or other manual review and will be recorded and tracked in the CTMS or other approved format. Telecommunications and other verbal communications regarding deviations will be considered and handled as important communication, documented and tracked as protocol deviations, as necessary.

Individual entries for protocol deviations that are recorded in the CTMS, or other approved format, following site monitoring and other manual reviews will be reviewed against the individual data points in the eCRF database but will not be formally reconciled with the eCRF database (e.g., their description or occurrence date). The overall procedure for managing protocol deviations are described in the SOPs of the CRO Data Management Confidentiality statement: Data and information contained in this document are considered to constitute trade secrets and confidential commercial information, and the legal protections provided to such trade secrets and confidential information are hereby claimed under the applicable provisions of applicable law. No part of this document may be publicly disclosed without the written consent of Philip Morris Products S.A.

Team. All deviations will be reviewed periodically, as determined at study start, to identify trends to improve monitoring and/or potential impact on the statistical analysis.

11.2 Data Handling

All study data will be managed by the Data Management Team at the CRO. The overall procedures for quality assurance of clinical study data are described in the SOPs of the CRO Data Management Team. The Data Management Team at CRO will prepare a DMP, to be reviewed and approved by the Sponsor, prior to the start of the study. This document will describe, in detail, the Data Management related procedures and processes.

All data of all subjects enrolled and screening failures who experience an AE during the study (from time of informed consent to end of the safety follow-up period) will be captured and stored in the study database.

All data collected during the study is property of the Sponsor irrespective of the location of the database and the Data Management CRO.

11.2.1 Data Validation

The data will be validated as defined in the DMP and Data Validation Specifications. Discrepancies will be reported as defined in DMP and Data Validation Plan.

Data queries will be raised for discrepant or missing data. All changes to data will be captured in the database with a comprehensive audit trail.

11.2.2 Coding

Adverse events, concomitant disease, medical/surgical history, and prior/concomitant medication will be classified according to the terminology of the latest version of the following dictionaries, at time of coding the first entry:

| | |
|--|--|
| Medical history: | Medical Dictionary for Regulatory Activities (MedDRA [®]) |
| Adverse events: | MedDRA [®] |
| Medications: | WHO Drug Dictionary Enhanced and Anatomical Therapeutic and Chemical classification system |
| THS 2.2 device issues and/or malfunctions: | C54451/Medical_Device_Problem_Codes_FDA_CDRH |

11.2.3 Database Lock

When all outstanding Data Management issues have been resolved and all validation, quality review, and cleaning activities are complete, the database or selected data is/are declared soft

locked. Access to change data in the soft-locked database or to change selected data at this time is limited.

After the data is reviewed by the Sponsor, resolution of all raised queries and QC of the changed data, database, or selected data upon Sponsor approval as applicable, is declared locked.

Any changes to the database after that time can only be made by written agreement between the Sponsor and the Data Management and Statistical Team at the CRO. Any of those changes must be documented in the database log file.

After study completion, the study database will be transferred to the Sponsor in the format specified in the DMP in Clinical Data Interchange Standards Consortium's Study Data Tabulation Model Data Structure Specifications.

12 PLANNED STATISTICAL METHODS

12.1 General Considerations

Full details of the statistical analysis will be given in a SAP. Any changes to the planned statistical methods will be documented in the CSR. The statistical evaluation will be performed using SAS[®], version 9.2 or later.

12.1.1 Stratification Criteria

For the primary analysis of the BoExp, the following stratification criteria will be used:

1. Sex (male; female).
2. Average daily CC consumption over the last 4 weeks as reported during Screening.

12.1.2 Definitions for Statistical Data Analysis

In general, baseline is the last available time-point prior to Day 1, 06:30 AM.

12.1.3 Descriptive Statistics

All data will be presented in listings, ordered by product arm and subject, unless otherwise specified.

Descriptive statistics for continuous variables (number of subjects [n], number and percent of subjects with data, mean, standard deviation [SD], median, first and third quartiles, minimum and maximum for continuous data, and the n and absolute and relative [%] frequency for categorical data) will be presented by product arm and overall at each time point, where applicable.

For BoExp, the geometric mean and coefficient of variation (CV) will be presented in addition to the mean and SD.

12.1.4 Handling of Missing Values and of Values outside the Detection Limits

Missing values for the BoExp will be imputed using the last observation carried forward approach.

For questionnaire data, total scores and domain or subscale scores may use a certain degree of imputation by averaging across individual item scores.

Values below the lower limit of quantification (LLOQ) will be imputed using 0.5 x LLOQ. For values above the upper limit of quantification (ULOQ), the ULOQ will be used for calculation and reporting in summary tables. The number of values below LLOQ or above ULOQ will be presented in each summary table.

Further details will be provided in the SAP.

Confidentiality statement: Data and information contained in this document are considered to constitute trade secrets and confidential commercial information, and the legal protections provided to such trade secrets and confidential information are hereby claimed under the applicable provisions of applicable law. No part of this document may be publicly disclosed without the written consent of Philip Morris Products S.A.

12.1.5 Significance Level for Inferential Analysis

Unless stated otherwise, all statistical tests will be two-sided and conducted at the 5% level, and all quoted confidence intervals (CIs) will be two-sided 95% CIs.

The primary endpoints will be tested using a multiple testing procedure to preserve the overall alpha level by simultaneously testing the endpoints using a closed procedure with each test performed at an alpha level of 5%. This implies that statistical significance is required for all primary endpoints in order to be able to make confirmatory claims about any of the endpoints.

Full details of this approach will be provided in the SAP.

12.2 Determination of Sample Size and Power Consideration

The following discussion addresses the ability to demonstrate on Day 5 a reduction of at least 50% on 4 selected primary BoExps in smokers switching from CC to THS 2.2 as compared to smokers continuing to smoke CC.

Table 16 describes the expected coefficients of variation (CV) and mean ratios (MR) between THS 2.2 and the two control arms based on data from a controlled, randomized, open-label, 3-arm parallel single-center confinement study that investigated exposure to selected smoke constituents in smokers switching from CC to smoking article cigarettes for 5 days, the YVD-CS01-EU study (ClinicalTrials.gov: ID: NCT00812279) sponsored by PMI.

**Table 16. Coefficients of Variation (YVD-CS01-EU study)**

| | THS 2.2 /CC MR (CV) | THS 2.2 /SA MR (CV) |
|--------|------------------------|------------------------|
| COHb | 0.40 (0.32) | 2.10 (0.20) |
| 3-HPMA | 0.30 (0.50) | 1.70 (0.33) |
| MHBMA | 0.15 (0.70) | 1.00 (0.35) |
| S-PMA | 0.20 (0.70) | 1.15 (0.42) |

Abbreviations: 3-HPMA = 3-hydroxypropylmercapturic acid; CC = conventional cigarettes; COHb = carboxyhemoglobin; CV = coefficients of variation; MHBMA = monohydroxybutenyl mercapturic acid; MR = mean ratios; S-PMA = S-phenylmercapturic acid; SA = smoking abstinence; THS 2.2 = Tobacco Heating System 2.2.

Table 17 describes the expected coefficients of variation (CV) and mean ratios (MR) between THS 2.2 and the CC control arm based on data from a single-center, open-label, randomized, controlled, 2-arm parallel group study to evaluate the exposure to selected smoke constituents in smoking, but otherwise healthy subjects switching from conventional cigarettes to THS 2.1 compared to subjects continuing to smoke CC for 5 days, the ZRHX-EX-01 study (ClinicalTrials.gov: ID: NCT01780714) sponsored by PMI.

**Table 17. Coefficients of Variation (ZRHX-EX-01 study)**

| | THS 2.2 /CC MR (CV) |
|--------|------------------------|
| COHb | 0.44 (0.14) |
| 3-HPMA | 0.28 (0.20) |
| MHBMA | 0.11 (0.47) |
| S-PMA | 0.07 (0.50) |

Abbreviations: 3-HPMA = 3-hydroxypropylmercapturic acid; CC = conventional cigarettes; COHb = carboxyhemoglobin; CV = coefficients of variation; MHBMA = monohydroxybutenyl mercaptyuric acid; MR = mean ratios; S-PMA = S-phenylmercapturic acid; THS 2.2 = Tobacco Heating System 2.2.

Based on these two sets of assumptions, the power to demonstrate a reduction was computed. Table 18 describes the expected power to demonstrate a reduction on 4 primary BoExps in smokers switching from CC to THS 2.2 as compared to those continuing to smoke CC, using one-sided test with 2.5% type I error probability using the assumptions from YVD-CS01-EU and ZRHX-EX-01 and 160 smokers (80 in THS 2.2, 40 in CC, and 40 in the SA arm).

**Table 18. Expected power (YVD-CS01-EU and ZRHX-EX-01 studies assumptions)**

| Assumptions | Reduction | | | | | |
|-------------|-----------|------|-----|-----|-----|-----|
| | 50% | 51% | 52% | 53% | 54% | 55% |
| YVD-CS01-EU | 96% | 91% | 85% | 75% | 63% | 48% |
| ZRHX-EX-01 | >99% | >99% | 96% | 81% | 48% | 16% |

A total of 160 smokers (80 in THS 2.2, 40 in CC, and 40 in the SA arm) will be randomized to demonstrate to demonstrate a reduction of at least 50% on 4 primary BoExps in smokers switching from CC to THS 2.2 as compared to those continuing to smoke CC, using one-sided test with 2.5% type I error probability.

Power considerations related to secondary endpoints of biological changes:

The sample size is sufficient to obtain 95% CIs for the ratio between (geometrical) mean levels of primary BoExps in THS 2.2 and SA see Section 12.2 with upper and lower limits deviating not more than 18% from the point estimates, with an 80% overall probability of achieving the desired precision of estimating the true mean.

This study has 80% power using a one-sided test with 2.5% type I error probability:

- To detect a 0.631 [ml/min/kg] (29%) difference between THS 2.2 and CC in CYP1A2 activity, as measured by the CAF clearance, assuming a standard deviation of 0.564. Effect size and variability are derived from data obtained in the YVD-CS01-EU study sponsored by PMI.
- To detect a 24.71 [ng/g creatinine] (20%) difference between THS 2.2 and CC in 11-DTX-B2, assuming a standard deviation of 43.78, as reported by Saareks et al, 2001. The anticipated effect size of THS 2.2 is assumed to be about 90% of the effect of smoking cessation reported in the paper by Saareks et al, 2001.

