Confidentiality statement: Data and information contained in this document are considered to constitute trade secrets and confidential commercial information, and the legal protections provided to such trade secrets and confidential information are hereby claimed under the applicable provisions of applicable law. No part of this document may be publicly disclosed without the written consent of Philip Morris Products S.A.

level, and all quoted confidence intervals (CIs) will be two-sided 95%CIs.

Sample Size:

A total of 160 subjects (80 in the THS 2.2 arm, 40 in the CC arm, and 40 in the SA arm) will be randomized. This sample size is needed to attain 80% power to show demonstrate a reduction of at least 50% on four primary BoExps in smokers switching from CC to THS 2.2 as compared to those continuing to smoke CC, using one-sided test with 2.5% type I error probability.

TABLE OF CONTENTS

| | |
|--|----|
| SYNOPSIS..... | 2 |
| TABLE OF CONTENTS..... | 13 |
| LIST OF ABBREVIATIONS AND DEFINITIONS OF TERMS..... | 17 |
| 1 ETHICS AND REGULATIONS..... | 23 |
| 1.1 Independent Ethics Committee Approval..... | 23 |
| 1.2 Ethical Conduct of the Study..... | 23 |
| 1.3 Subject Information and Consent..... | 24 |
| 1.4 Good Clinical Practice and Regulatory Requirements..... | 25 |
| 2 INTRODUCTION..... | 26 |
| 2.1 Background..... | 26 |
| 2.2 Purpose of the Study..... | 28 |
| 2.3 Anticipated Benefits and Risks..... | 28 |
| 3 STUDY OBJECTIVES..... | 30 |
| 3.1 Primary Objective..... | 30 |
| 3.2 Secondary Objectives..... | 30 |
| 3.3 Exploratory Objectives..... | 30 |
| 3.4 Study Endpoints..... | 31 |
| 4 INVESTIGATIONAL PLAN..... | 36 |
| 4.1 Overall Study Design and Plan..... | 36 |
| 4.2 Rationale for Study Design and Control Groups..... | 38 |
| 4.3 Appropriateness of Measurements..... | 39 |
| 4.4 Study Duration..... | 40 |
| 5 STUDY POPULATION..... | 41 |
| 5.1 Selection of Study Population..... | 41 |
| 6 INVESTIGATIONAL PRODUCTS..... | 48 |
| 6.1 Description of Investigational Products..... | 48 |
| 6.2 Use of Investigational Product(s)..... | 49 |
| 6.3 Method for Assigning Subjects to Study Arms..... | 51 |
| 6.4 Blinding..... | 51 |
| 6.5 Investigational Product Accountability and Compliance..... | 52 |
| 6.6 Restrictions..... | 53 |
| 6.7 Concomitant Medication..... | 54 |

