12.4 Primary Analysis

12.4.1 Primary Endpoint Analysis Variables

The primary endpoints are:

- COHb on Day 5
- MHBMA on Day 5
- 3-HPMA on Day 5
- S-PMA on Day 5.

See section 3.4.1.

Evaluation Criterion: The study will be considered successful if the study demonstrates a 50% reduction or more for all four primary BoExp in the THS 2.2 arm compared to the CC arm (as measured on Day 5), using a one-sided test with 2.5% type I error probability.

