8 SAMPLE SIZE JUSTIFICATION

The following discussion addresses the ability to demonstrate on Day 5 a reduction of at least 50% on four selected primary BoExp in smokers switching from CC to THS 2.2 as compared to smokers continuing to smoke CC.

Table 11 describes the expected coefficients of variation (CV) and mean ratios (MR) between THS 2.2 and the two control arms in COHb, 3-HPMA, MHBMA and S-PMA on Day 5 based on data from a controlled, randomized, open-label, 3-arm parallel single-center confinement study that investigated exposure to selected smoke constituents in smokers switching from CCs to smoking article (SMAR) cigarettes for 5 days, the YVD-CS01-EU study (ClinicalTrials.gov: ID: NCT00812279) sponsored by PMI. The mean ratios and CVs for SMAR/CC are expected to be the same as THS 2.2/CC.

Table 11: Coefficients of Variation (YVD-CS01-EU study)

	THS 2.2 /CC MR (CV)	THS 2.2 /SA MR (CV)
COHb	0.40 (0.32)	2.10 (0.20)
3-HPMA	0.30 (0.50)	1.70 (0.33)
MHBMA	0.15 (0.70)	1.00 (0.35)
S-PMA	0.20 (0.70)	1.15 (0.42)

Abbreviations: 3-HPMA = 3-hydroxypropylmercapturic acid; CC = conventional cigarettes; COHb = carboxyhemoglobin; CV = coefficient of variation; MHBMA = monohydroxybutenyl mercaptyuric acid; MR = mean ratio; S-PMA = S-phenylmercapturic acid; SA = smoking abstinence; THS 2.2 = Tobacco Heating System 2.2.

Table 12 describes the expected CV and MR between THS 2.2 and the CC control arm in COHb, 3-HPMA, MHBMA, S-PMA based on data from a single-center, open-label, randomized, controlled, 2-arm parallel group study to evaluate the exposure to selected smoke constituents in smoking, apparently healthy subjects switching from CC to THS 2.1 compared to subjects continuing to smoke CC for 5 days, the ZRHX-EX-01 study (ClinicalTrials.gov: ID: NCT01780714) sponsored by PMI. The mean ratios and coefficients of variations for THS 2.1/CC are expected to be the same as THS 2.2/CC.

Table 12: Coefficients of Variation (ZRHX-EX-01 study)

	THS 2.2 /CC MR (CV)
COHb	0.44 (0.14)
3-HPMA	0.28 (0.20)
MHBMA	0.11 (0.47)
S-PMA	0.07 (0.50)

Abbreviations: 3-HPMA = 3-hydroxypropylmercapturic acid; CC = conventional cigarettes; COHb = carboxyhemoglobin; CV = coefficients of variation; MHBMA = monohydroxybutenyl mercaptyuric acid; MR = mean ratios; S-PMA = S-phenylmercapturic acid; THS 2.2 = Tobacco Heating System 2.2.

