**Table 13: Expected Power (YVD-CS01-EU and ZRHX-EX-01 Studies Assumptions)**

Assumptions	Reduction					
	50%	51%	52%	53%	54%	55%
YVD-CS01-EU	96%	91%	85%	75%	63%	48%
ZRHX-EX-01	>99%	>99%	96%	81%	48%	16%

A total of 160 smokers (80 in THS 2.2, 40 in CC, and 40 in the SA arm) will be randomized to demonstrate a reduction of at least 50% on 4 primary BoExp in smokers switching from CC to THS 2.2 as compared to those continuing to smoke CC, using one-sided test with 2.5% type I error probability.

The sample size is sufficient to obtain 95% CIs for the ratio between (geometrical) mean levels of primary BoExp in THS 2.2 and SA with upper and lower limits deviating not more than 18% from the point estimates, with an 80% overall probability of achieving the desired precision of estimating the true mean.

This study has 80% power using a one-sided test with 2.5% type I error probability:

1. To detect a 0.631 [mL/min/kg] (29%) difference between THS 2.2 and CC in CYP1A2 activity, as measured by the CAF clearance, assuming a standard deviation (SD) of 0.564. Effect size and variability are derived from data obtained in the YVD-CS01-EU study sponsored by PMI.
2. To detect a 24.71 [ng/g creatinine] (20%) difference between THS 2.2 and CC in 11-DTX-B2, assuming a SD of 43.78. The anticipated effect size of THS 2.2 is assumed to be about 90% of the effect of smoking cessation.

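### The ZRHX-EX-01 power row does not follow from its printed COHb inputs (68% against 81% at a 53% reduction), and the synopsis's 80% power contradicts the 96% and >99% in Section 12.2

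*Protocol*

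**What the plan says.** Protocol Section 12.2 bases the primary power on two earlier studies. For ZRHX-EX-01, which tested THS 2.1, Table 17 gives the COHb input as "COHb | 0.44 (0.14"), meaning a THS/CC mean ratio of 0.44 and a CV of 0.14. The other three biomarkers have mean ratios of 0.28 or less.

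The power is computed "using one-sided test with 2.5% type I error probability using the assumptions from YVD-CS01-EU and ZRHX-EX-01 and 160 smokers", of whom 80 are in the THS 2.2 arm and 40 in the CC arm. Table 18 prints the result for reductions of 50, 51, 52, 53, 54 and 55% as "ZRHX-EX-01 | >99% | >99% | 96% | 81% | 48% | 16"%. The YVD-CS01-EU row beside it reads 96, 91, 85, 75, 63 and 48%.

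SAP Section 8 repeats the inputs (Table 12) and the row (Table 13: "ZRHX-EX-01 >99% >99% 96% 81% 48% 16"%). It adds: "The mean ratios and coefficients of variations for THS 2.1/CC are expected to be the same as THS 2.2/CC".

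The protocol synopsis, under Sample Size, says: "This sample size is needed to attain 80% power to show demonstrate a reduction of at least 50% on four primary BoExps". In Section 12.2 the 80% figure belongs to other targets. One is the precision of the THS 2.2/SA ratios ("with an 80% overall probability of achieving the desired precision of estimating the true mean"); the others are the detectable differences for CYP1A2 and 11-DTX-B2.

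**The concern.** The inputs, sample size, test and resulting power are all printed, so the row can be checked. One row follows from its inputs and the other does not. Either a COHb input, the group sizes behind the row, or the row itself is misprinted, and the SAP carries the same discrepancy.

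ZRHX-EX-01 matters because it tested the immediate predecessor of the study product, and the SAP expects the same ratios and CVs for THS 2.2. In its 53% column the discrepancy spans the usual 80% line: 81% printed, 68% recomputed.

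The synopsis adds a second inconsistency. A reader who sees only the synopsis concludes that 160 subjects just reach 80% power for the primary test. Section 12.2 gives 96% or more for the same criterion, test and sample size.

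**Working it through.** **Inputs.** One-sided alpha 0.025; 80 THS 2.2 and 40 CC subjects (Protocol 12.2). Analysis on the natural log scale (12.4.4). Mean ratios (MR) and CVs from Tables 16 and 17. No dropout allowance is stated, so none is applied.

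**Formulas.** For each biomarker:
- log-scale SD: s = sqrt(ln(1 + CV²))
- standard error: SE = s × sqrt(1/80 + 1/40) = s × 0.19365
- difference to detect a reduction of at least R: d = ln((1 − R)/MR)
- power: noncentral t, 118 degrees of freedom, noncentrality d/SE

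Joint power is the product over the four biomarkers, which assumes independence.

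**Step 1: reproduce the plan's own YVD-CS01-EU row.** For COHb, MR 0.40 and CV 0.32 give s = 0.3122 and SE = 0.0605. At 53%, d = ln(0.47/0.40) = 0.1613 and d/SE = 2.67. Joint power is 75.2%; 75% is printed. The first two rows of the table below compare all six columns. The method is therefore the plan's own, or numerically equivalent to it.

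**Step 2: the same method with the Table 17 inputs.** For COHb, MR 0.44 and CV 0.14 give s = sqrt(ln 1.0196) = 0.1393 and SE = 0.0270. At 53%, d = ln(0.47/0.44) = 0.0660 and d/SE = 2.44. Power is 67.9% (normal approximation 68.6%); 81% is printed. The other three biomarkers have essentially 100% power in every column, so COHb alone sets this row and the independence assumption is immaterial.

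| Power, % | 50% | 51% | 52% | 53% | 54% | 55% |
|---|---|---|---|---|---|---|
| YVD-CS01-EU, printed | 96 | 91 | 85 | 75 | 63 | 48 |
| YVD-CS01-EU, recomputed | 95.5 | 91.4 | 84.8 | 75.2 | 62.8 | 48.5 |
| ZRHX-EX-01, printed | >99 | >99 | 96 | 81 | 48 | 16 |
| ZRHX-EX-01, recomputed (CV 0.14) | 99.7 | 97.7 | 89.2 | 67.9 | 37.2 | 12.8 |
| COHb CV 0.12, 80+40 | >99.9 | 99.6 | 96.1 | 80.7 | 47.8 | 15.9 |
| COHb CV 0.14, 110+55 | >99.9 | 99.6 | 96.4 | 81.3 | 48.4 | 16.1 |

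**Step 3: try to explain the gap.**
- Normal approximation: 99.7, 97.9, 89.7, 68.6, 37.7, 13.0.
- CV used directly as the log SD: 88.9, 67.5, 36.9, 12.8 at 52% to 55%.
- One-sided alpha 5%: 94.1, 78.4, 49.7, 20.7 at 52% to 55%.
- Rounding: with MR anywhere in 0.435–0.445 and CV in 0.135–0.145, the best fit to the row is MR 0.4375 with CV 0.135. It gives 94.2, 78.0, 48.1 and 18.8 at 52% to 55%, still up to 3.0 points off.

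None of these recovers the row. A COHb CV of about 0.12 does, and so does CV 0.14 with about 110 and 55 subjects. The documents do not show which, if either, was used.

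**Step 4: the synopsis.** At the 50% criterion with 2:1 allocation, about 80% joint power takes 50+25 THS 2.2 and CC subjects under YVD-CS01-EU (81.4%) and 30+15 under ZRHX-EX-01 (81.0%). The plan has 80+40, with 96% and >99% printed. The 80% therefore describes neither the power achieved on the primary test nor the reason for 160 subjects.

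**The case against.** **Two-decimal inputs should not be treated as exact.** Within the rounding of MR and CV, power in the 53% column runs from about 49% to 84%. MR 0.436 with CV 0.136 gives 81.1% there. Taken singly, every printed cell lies inside its own range. This stands as a caution: the 68% is what the printed inputs give, and it is sensitive to the unrounded MR. It does not rescue the row, because one pair of values must produce all six cells. MR 0.436 with CV 0.136 gives 52.7% and 22.2% at 54% and 55%, against 48% and 16% printed. The YVD-CS01-EU row follows from its two-decimal inputs, which suggests, though it does not prove, that rounded inputs were used.

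**No decision rests on the 51% to 55% columns.** Success requires that the study "demonstrates a 50% reduction or more for all four primary BoExp in the THS 2.2 arm compared to the CC arm", and the 50% column agrees. This is right, and it limits the weight of the point.

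**The synopsis's 80% may be a design minimum that 96% and >99% both satisfy.** Power is indeed understated rather than inflated. But the sentence says the sample size is needed for that power, which the plan's own figures contradict. The THS 2.2/SA precision target does support the planned size: with the Table 16 SA CVs, assuming independence and taking the upper limit within 18%, the probability is 86.8% at 80+40, 81.6% at 78+39 and 1.1% at 50+25.

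**Conclusion.** Both inconsistencies are real. The ZRHX-EX-01 row in Protocol Table 18 and SAP Table 13 does not follow from the inputs in Protocol Table 17 and SAP Table 12. If CV 0.14, MR 0.44 and 80+40 are right, the row is overstated by up to 13 points (81% against 68% at 53%). If the source CV is about 0.12, the row is right and the input tables are wrong. The synopsis gives 80% for a test to which Section 12.2 assigns 96% and >99%.

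The calculation assumes log-normal data, a common log-scale SD and no dropout; the match on the YVD-CS01-EU row supports the method.

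The consequence is one of reporting. Power at the 50% success criterion is 99.7% from the printed inputs. The largest reduction with at least 80% power under both data sets stays at 52%, because YVD-CS01-EU already sets that limit (85% at 52%, 75% at 53%). The adequacy of 160 subjects is not in question.

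**What to change.** Check the unrounded COHb mean ratio, the CV and the group sizes used for this row against the ZRHX-EX-01 data and the original calculation. Then:

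- If MR 0.44, CV 0.14 and 80+40 are confirmed, print >99%, 98%, 89%, 68%, 37% and 13% in Protocol Table 18 and SAP Table 13.
- If the CV is 0.12, correct Protocol Table 17 and SAP Table 12 and keep the row.
- If the source shows something else, such as other group sizes or an unrounded mean ratio that differs from 0.44, recompute the row for 80+40 from those values and print the inputs to enough decimals to reproduce it.

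In the synopsis, replace the 80% statement with: 160 subjects give about 96% (YVD-CS01-EU assumptions) and >99% (ZRHX-EX-01 assumptions) power to demonstrate a reduction of at least 50% on all four primary biomarkers, one-sided 2.5%. Keep 80% for the precision, CYP1A2 and 11-DTX-B2 statements in Section 12.2.

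The cost is one source check and a few restated figures. Enrolment, test and success criterion stay as they are.
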